Neuropathic pain in SCI is common, impactful, and difficult to treat. Gabapentin is effective in the management of symptoms and concerns related to SCI including motor recovery, spasticity, and mood among others. This makes gabapentin an important pharmacologic intervention, which compels providers to define treatment guidelines related to its use. One aspect of which should relate to the timing of initiation of therapy. The goal of this study is to determine whether early initiation of treatment with gabapentin will decrease average pain scores and opiate use when compared to late initiation of treatment with gabapentin in the population with acute SCI. Gabapentin, although used commonly, is not started in all patients with acute SCI but is often started at the onset of neuropathic pain. If gabapentin is found to be more effective when initiated early, it would be reasonable to start gabapentin immediately following acute SCI in all patients in whom it is not otherwise contraindicated.

1. Objectives

- Primary

- To determine if the time from injury influences the prevalence of neuropathic pain in acute SCI
- To determine if the use of gabapentin in the early acute period influences the prevalence of neuropathic pain in patients with acute SCI
- To compare the efficacy of acute versus subacute initiation of gabapentin in treating neuropathic pain in SCI

- Secondary

- To compare the overall pain scores
- To determine the prevalence of neuropathic pain in those with SCI at admission and discharge to the inpatient rehabilitation hospital
- To compare the use of opiates
- To compare the average daily change in Functional Independence Measure (FIM)
- To compare the change in total motor score on the ASIA impairment scale
- To identify side effects of treatment with gabapentin and their frequency

2. Endpoints

Primary

- Presence of neuropathic pain at time of enrollment and again around time of discharge (Douleur Neuropathique 4, DN4)
- Neuropathic pain level (Neuropathic Pain Scale, NPS) at time of enrollment and again around time of discharge

Secondary

- Average pain level recorded in nursing flowsheet (Numeric Pain Rating Scale, NPRS)
- Weekly total use of opiates (total morphine milligram equivalents, MME)
- Change in FIM during rehabilitation
- Change in total motor score on the ASIA impairment scale during entire rehabilitation course

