- Side effects attributed directly to gabapentin in physician documentation and whether or not gabapentin was stopped due to these side effects

3. Design

- Prospective, observational, cohort, single center study
- The study will enroll subjects with acute spinal cord injury who are admitted to acute inpatient rehabilitation at MetroHealth Rehabilitation Institute (MRI).

- After enrollment, subjects will be followed through the end of their acute rehabilitation stay including any interruption in rehabilitation for which they require ED evaluation and/or acute hospital readmission so long as they return to MRI.
- Around the time of enrollment, subjects will be asked to complete the DN4 questionnaire and the NPS.
- Around the time of discharge, subjects will be asked to complete a second DN4 questionnaire and the NPS.
- The remainder of the data collection will be through review of the patient's electronic medical record (EMR).
- Patients will be divided into those who first received gabapentin during their acute inpatient hospitalization, prior to admission to acute rehabilitation, and those who did not. Additionally, the timing of gabapentin initiation will also be recorded.

4. Subject selection

- Study population

Subjects are patients who suffered acute spinal cord injury for which they are admitted to acute inpatient rehabilitation at MRI.
- Inclusion criteria

Subjects who meet all the following criteria may be given consideration for inclusion in this clinical investigation, provided no exclusion criterion is met

 1. Clinical diagnosis of acute spinal cord injury
 2. Admission to MRI for acute inpatient rehabilitation
- Exclusion criteria

Subjects who meet one or more of the following criteria will be excluded from this clinical study.

 1. Unable to communicate verbally or by writing, unable to follow basic instructions, or unable to answer questions regarding their symptoms

5. Subject Accountability

- Point of enrollment

The point of enrollment is the time at which time a subject signs and dates the valid, IRB approved informed consent form. No study-related procedure or assessments can take place until the informed consent form is signed.
- Withdrawal

All subjects enrolled to the study (including withdrawal or lost to follow-up) shall be accounted for and documented.

Reasons for withdrawal include:

 1. Physician discretion
 2. Subject choice
 3. Lost to follow up
 4. Death

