Subjects may withdraw from the study at any time, with or without reason without prejudice to further treatment.

6. Study methods

- Pre-screening

To determine eligibility for enrollment into the study, the inclusion and exclusion criteria must be assessed.

- Informed consent

After a patient has been identified as a potential candidate, based on meeting all inclusion and no exclusion criteria, written Informed Consent must be obtained by asking patients to read and review the valid IRB-approved Informed Consent. The informed consent process will abide by the MetroHealth Medical Center IRB process.

- Initial Visit

The initial visit will occur at or within 7 days of the time of enrollment and admission to rehabilitation

- o Visit Type: Visit to patient while they are admitted to hospital
 - Admission DN4 and NPS

- Final Visit

The final visit will occur at or within 7 days of the time of discharge from MRI

- o Visit Type: Visit to patient while they are admitted to hospital
 - Discharge DN4 and NPS

- Additional data collection: As outlined in Figure 2

The data collection will be completed via review of the EMR of each subject, and will include the following:

- o Demographics
 - Age
 - Sex
 - Race
 - History of drug use
 - History of smoking
- o Home pain medications prior to SCI injury
- o Date of injury
- o ASIA impairment scores (AIS; 1st documented AIS, rehabilitation admission AIS, and rehabilitation discharge AIS)
- o Operative vs nonoperative management of SCI
- o Length of stay in rehabilitation
- o Rehabilitation admission and discharge FIM scores
- o Rehabilitation admission and discharge total motor scores (TMS) as recorded on AIS
- o Pain scores (NPRS)
 - Average score per week from injury as documented in EMR
- o Opiate use
 - Total weekly MME per week from injury

- Side effects
 - Record side effects attributed to gabapentin by treating physician
 - Record if therapy was stopped and why (ineffective, no longer required, adverse reaction)

7. Statistical Analysis Plan

Subject demographics will be summarized by typical descriptive statistics to compare means or medians and measures of variability

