The relationship between the presence of neuropathic pain and: 1) the time from injury; 2) the timing of gabapentin initiation will be evaluated by building logistic regression models with dichotomous neuropathic pain (measured by DN4) as the dependent variable and time as the independent variable. Potential confounding variables will be added to the model if independently associated with the outcome of interest or based on theoretical grounds.

The efficacy of gabapentin by timing of initiation will be analyzed with a regression model with change in pain on the Neuropathic Pain Scale from admission to discharge with timing of gabapentin initiation as the independent variable. Potential confounding variables will be added to the model if independently associated with the outcome of interest or based on theoretical grounds.

8. Data analysis

- All enrolled subjects will be eligible for evaluation.

9. Data Safety/ Monitoring

The PI and co-investigators will monitor the progress of the research study, including assessments of data quality, participant recruitment, accrual and retention, subject's confidentiality, any adverse event(s), and external factors or relevant information that might have an impact on the safety or ethics of the study.

After recruitment, data analysis will occur and any changes to the risk/benefit ratio to study participation will be identified and reported to the IRB. In addition, the PI and co-investigators will meet on an annual basis and reports of the meeting will be submitted to the IRB.

If an adverse event occurs, it will be reported immediately to the MetroHealth Institutional Review Board (IRB). If an unexpected adverse event occurs, the investigators will assess the risk/benefit ratio of the study and submit any modifications deemed necessary to the IRB for approval. At the time of the IRB renewal, the PI will

submit information about the frequency of the monitoring, the dates that the monthly meeting took place, a summary of the cumulative adverse events, external factors or relevant information that might have an impact on the safety or the ethics of the study, and final conclusions regarding changes to the anticipated risk/benefit ratio to study participation and final recommendation related to the continuation, changing, or termination of the study.

10. Study Assessments

1. Assessment of presence of neuropathic pain (DN4) at time of admission and discharge

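### For some patients who start gabapentin in rehabilitation, the admission NPS may predate the pain being treated, so the planned NPS change mixes pain onset with treatment response and can score real relief as worsening.

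*Combined protocol and SAP*

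**What the plan says.** The third primary objective (section 1) is "To compare the efficacy of acute versus subacute initiation of gabapentin in treating neuropathic pain in SCI". Section 7 serves it with a regression of "change in pain on the Neuropathic Pain Scale from admission to discharge with timing of gabapentin initiation as the independent variable".

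Section 6 fixes when the NPS is taken. The first rating: "The initial visit will occur at or within 7 days of the time of enrollment and admission to rehabilitation". The second: "The final visit will occur at or within 7 days of the time of discharge from MRI". No NPS is planned between these visits, and neither is tied to the first dose of gabapentin or to the onset of pain.

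The inclusion criteria in section 4 are two: "Clinical diagnosis of acute spinal cord injury" and admission to the rehabilitation unit. Neuropathic pain is not required, and section 8 makes every enrolled subject eligible for evaluation. The Introduction says of gabapentin that it "is not started in all patients with acute SCI but is often started at the onset of neuropathic pain".

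Section 3 splits patients by whether the first dose came in the acute stay, with everyone else in the second group: "Patients will be divided into those who first received gabapentin during their acute inpatient hospitalization, prior to admission to acute rehabilitation, and those who did" (sentence cut short here). On the start date it says: "Additionally, the timing of gabapentin initiation will also be recorded". Section 7 allows confounders into the model on an empirical or theoretical basis, but names neither admission NPS nor admission DN4 status.

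**The concern.** A change score measures response only if its baseline reflects the condition that treatment was started for. Take a patient who has no neuropathic pain at the admission visit, develops it during the stay, starts gabapentin and is rated again at discharge. The planned change is the rise in pain plus the later relief. Unless relief is nearly complete, the patient counts as having worsened. A patient who starts shortly before discharge contributes the whole rise and almost no time on drug.

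The third primary objective concerns treating pain. The first two concern its prevalence and have their own DN4 models. If onset enters the NPS change, the efficacy result no longer separates the two questions. The Introduction says that a finding in favour of early start would make it reasonable to begin gabapentin immediately after injury in all patients without a contraindication, so the meaning of this coefficient matters.

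**Working it through.** The plan states no sample size, effect size, standard deviation or expected share of late-onset pain, so there is no figure of its own to reproduce. The check is the arithmetic of the planned change score.

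**Inputs (all assumed; the documents give none)**
- P = NPS when gabapentin is started: 60, on an assumed 0–100 scale
- r = true proportional relief by discharge, the same in both groups: 0.5
- f = share of rehabilitation starters whose pain began after the admission NPS, with an admission score of about 0: 0 to 1
- ra = share of P already relieved by rehabilitation admission in acute-stay starters: 0 to 0.5

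**One patient with onset after the first visit**
- Discharge score = (1 − r)P = 0.5 × 60 = 30
- Planned change = 30 − 0 = +30 (worsening)
- Change from start of treatment = 30 − 60 = −30 (true response)

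**Late-group mean**

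Mean planned change = f(1 − r)P + (1 − f)(−rP) = P(f − r). The true response is −rP = −30, so the error is fP = 60f.

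| f | Planned mean change | Error |
|---|---|---|
| 0 | −30 | 0 |
| 0.25 | −15 | +15 |
| 0.50 | 0 | +30 |
| 0.75 | +15 | +45 |

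The late group shows no mean improvement once f reaches r.

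**Early-versus-late contrast**

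Acute-stay starters are already on drug at their admission rating, so their planned mean change is −(r − ra)P. With equal true efficacy, late minus early = P(f − r) + (r − ra)P = P(f − ra). A positive value makes late start look worse.

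| f | ra = 0 | ra = 0.25 | ra = 0.5 |
|---|---|---|---|
| 0 | 0 | −15 | −30 |
| 0.25 | +15 | 0 | −15 |
| 0.50 | +30 | +15 | 0 |
| 0.75 | +45 | +30 | +15 |
| 1 | +60 | +45 | +30 |

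The range is −30 to +60, so the sign is not settled.

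**Effect of adjusting for admission NPS**

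This was simulated with 200,000 patients per scenario, score at start with mean 60 and SD 12, admission score about 3 in late-onset patients, and discharge noise SD 8. Over 99% of late-onset patients were scored as worse. The late-minus-early coefficient, true value 0, was:

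| f | ra | Unadjusted | Adjusted for admission NPS |
|---|---|---|---|
| 0.25 | 0 | +14.1 | +2.1 |
| 0.50 | 0 | +28.5 | +3.0 |
| 0.75 | 0 | +42.7 | +4.8 |
| 0 | 0.25 | −15.0 | −8.4 |

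Adjustment removes most of the late-onset error in this set-up, but not all. It removes less of the error from relief before admission.

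**Moving only the late starters' baseline to the first dose**

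Late minus early becomes −rP + (r − ra)P = −ra × P: −15 at ra = 0.25 and −30 at ra = 0.5. One error is exchanged for another.

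**The case against.** Four counter-arguments have weight.

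1. *The share may be small.* A reader might infer that the typical rehabilitation starter is free of neuropathic pain at the first visit. The documents do not support this. They say that gabapentin is often started at pain onset, but not when onset falls relative to rehabilitation admission, nor how long patients stay. The first visit may come up to 7 days after admission, so onsets in the first week can be captured. At f = 0 the late-group error is zero. What stands is that the plan does nothing to exclude or identify such patients.

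2. *The bias need not favour early start.* A reader might infer that the model will make late initiation look worse. The second table shows otherwise: relief obtained before admission is lost from the early group's change. Only an error of unknown size and sign is established.

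3. *Pain that emerges before a late start is a real consequence of waiting.* This is true for early versus late start as a strategy, and for the prevalence objectives, which the DN4 model serves. It does not rescue the NPS change as a measure of efficacy in treating pain, which is how the third objective and section 7 use it.

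4. *The plan already collects much of what is needed.* DN4 and NPS at both visits, the start date and weekly NPRS are recorded, and the confounder clause could admit admission NPS. This is correct, and it is why most of the remedy is wording. But section 7 commits to none of it, and the NPRS is a general pain score from nursing records that the plan does not link to gabapentin start.

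**Conclusion.** The point holds in a limited form. For rehabilitation starters whose neuropathic pain begins after the admission NPS, the planned outcome combines onset with response and can record real relief as worsening. Late starters already in pain at the first visit and not yet on drug do not have this problem.

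The figures of +15, +30 and +45 points are errors in the late-group mean only, for f of 25%, 50% and 75%. They rest on assumed scores of 0, 60 and 30 and on equal benefit in both groups. The share f is unknown, so the actual size is too. The net bias in the early-late contrast is P(f − ra), −30 to +60 points over the ranges shown, with no settled direction. This warrants a correction to the analysis plan. It does not show that the study will favour early initiation.

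**What to change.** Amend section 7, using data already collected, for the objective on efficacy in treating pain:

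- Do not use the admission NPS as the treatment baseline for patients who were DN4-negative at admission and started gabapentin after the initial visit.
- Report new onset in these patients (DN4 negative to positive) separately from response.
- Prespecify admission NPS and admission DN4 status as covariates in the NPS model.
- Report days from gabapentin start to the discharge NPS.
- State that early starters' baseline is on treatment, so the contrast does not compare full response in both groups. This is needed even after the other changes: setting aside the late-onset patients corresponds to f = 0 above, where −ra × P remains before adjustment.

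Where feasible, an NPS near the first dose may be added for rehabilitation starters. It should describe response within that group only, and not serve as a one-sided baseline for the early-late contrast. It would need prompt notice of new gabapentin orders, which the protocol does not provide for, and some ratings would be missed.

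The cost of the section 7 changes is fewer patients in the response analysis and slightly more analysis work. No new visit is needed unless the optional rating is adopted. The DN4 models for the prevalence objectives stay as they are.

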Protocol Title:

Comparison of Timing of Initiation on the Efficacy of Gabapentin in Treating
Neuropathic Pain in Spinal Cord Injury (SCI).

2/4/20

ClinicalTrials.gov Identifier: NCT04256603

Introduction:

Neuropathic pain is a common complaint in those with spinal cord injury (SCI) that has a significant negative effect on quality of life. This makes the treatment of neuropathic pain a priority in the SCI population. Efficacy of various treatments, however, remains controversial. There is evidence to support that gabapentin and pregabalin have some benefit in reducing neuropathic pain (1). Other positive effects of gabapentin on those with SCI have also been demonstrated. However, there has not been a study on the influence of timing of initiation of gabapentin on the efficacy of using it to treat neuropathic pain in the SCI population. Such a finding could change the standard of care in treatment of acute SCI.

The pooled prevalence of neuropathic pain post spinal cord injury is 53% (2). Not only common, neuropathic pain is pervasive, affecting aspects of patients' lives including sleep, physical function, and mood that in turn impact their activities—work and recreational alike (3). Thus, neuropathic pain management contributes to quality of life for a majority of people with SCI.

Although a high priority, the treatment of neuropathic pain in SCI remains notoriously difficult (4). Treatment options may be divided into pharmacologic and non-pharmacologic. Pharmacologic agents studied include amitriptyline, gabapentin, pregabalin, opiates, lidocaine, ketamine, valproate, lamotrigine, levetiracetam and carbamazepine; the most studied of which are amitriptyline, gabapentin, and pregabalin (5).

Gabapentin's potential is not limited to neuropathic pain management, making it a particularly compelling treatment option in the population with acute SCI. Gabapentin leads to improvement in total motor scores (6-9), reduced spasticity, reduced autonomic dysreflexia, and improved mood (8, 9). Animal models suggest it may be neuroprotective in the acute phase of injury (10). In those who undergo spine surgery, regardless of presence of SCI, gabapentin given perioperatively leads to reduced opiate use and decreased pain in post-operative period (11). Additionally, when compared to narcotic alternatives, gabapentin has minimal side effects.

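### The exposure rule and the timing models do not say how to handle pre-injury gabapentin users, pregabalin-only patients or never-users, so the early-versus-late contrast can be biased in either direction

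*Combined protocol and SAP*

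**What the plan says.** **Grouping.** Section 3 (Design) says patients are "divided into those who first received gabapentin during their acute inpatient hospitalization, prior to admission to acute rehabilitation, and those who did not". It continues: "Additionally, the timing of gabapentin initiation will also be recorded".

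**Who is in.** Section 4 has one exclusion criterion: "Unable to communicate verbally or by writing, unable to follow basic instructions, or unable to answer questions regarding their symptoms". Prior gabapentin or pregabalin use is not an exclusion, and section 8 makes every enrolled patient eligible for analysis.

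**What is collected.** Section 6 opens its list with "Additional data collection: As outlined in Figure 2". The list in the text includes "Home pain medications prior to SCI injury", weekly opiate totals, and whether and why gabapentin was stopped. It has no entry for pregabalin given after injury and none for the date gabapentin was stopped.

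**What is analysed.** One primary objective in section 1 is "To determine if the use of gabapentin in the early acute period influences the prevalence of neuropathic pain in patients with acute SCI"; another compares acute with subacute starting. Section 7 plans a logistic model for DN4 status and a regression for change in NPS, each with the time of starting gabapentin as the independent variable. Confounders may be added if they are associated with the outcome or justified by theory; none is named.

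**What the plan believes about pregabalin.** The Introduction states: "There is evidence to support that gabapentin and pregabalin have some benefit in reducing neuropathic pain".

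**The concern.** The comparison group in section 3 is defined only by not being in the first group. A patient taking gabapentin at home before injury did not first receive it in the acute hospital, so the wording places that patient with the late starters and never-users. That patient is a continuing user and informs neither an early nor a late start. A patient given only pregabalin in acute care goes to the same group, although the plan itself regards pregabalin as active.

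The section 7 models do not remove the difficulty. A model with start time as regressor needs a value for every patient, and the plan gives none for someone who started before injury or never started. Unless this is settled beforehand, the choice will be made during analysis.

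At stake is the use foreseen in the Introduction: if early starting looks better, gabapentin would be started right after injury in all patients without a contraindication. That inference needs a contrast between people who differ in when they newly started the drug.

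**Working it through.** The plan states no sample size, power, effect size or rate of prior gabapentinoid use, so it has no figure of its own to reproduce. The check is first a reading of the rules, then a short calculation on the direction of bias.

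**Step 1. Where each kind of patient falls.**

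| Patient | Section 3 split | Section 7 start-time regressor |
|---|---|---|
| First gabapentin in acute hospital | Early | Defined |
| First gabapentin in rehabilitation | Comparison | Defined |
| Never on gabapentin or pregabalin | Comparison | No value; coding not stated |
| On gabapentin before injury | Comparison, on the literal wording | Before injury; coding not stated |
| Pregabalin only, after injury | Comparison | No value; coding not stated |

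Sections 4 and 8 remove none of these patients. Home medications could enter through the general confounder rule. Pregabalin after injury could not, unless Figure 2 adds it to the data collected.

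**Step 2. Direction of bias in a two-group DN4 comparison.**

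Let pc be the neuropathic pain rate in the intended comparison patients, pe the rate in early starters, f the share of the comparison group made up of misplaced patients, and px their pain rate. The observed difference is

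D_obs = (1 − f)·pc + f·px − pe = (pc − pe) + f·(px − pc).

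The sign of the error is the sign of px − pc, which the documents do not give.

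Inputs, for illustration only: pc = 53%, the pooled prevalence after SCI in the Introduction, used here as a placeholder. pe = 38%, f and px are assumptions. The undisturbed difference is 53 − 38 = 15 points.

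| f | px = 38% (outcomes like early starters) | px = 70% (more pain) |
|---|---|---|
| 10% | 15 + 0.10 × (38 − 53) = 13.5 | 15 + 0.10 × (70 − 53) = 16.7 |
| 20% | 15 + 0.20 × (38 − 53) = 12.0 | 15 + 0.20 × (70 − 53) = 18.4 |
| 30% | 15 + 0.30 × (38 − 53) = 10.5 | 15 + 0.30 × (70 − 53) = 20.1 |

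**Step 3. The other reading of the rule.** If first receipt means the first dose after injury, continuing home users who are given gabapentin in the acute hospital join the early group instead. With g their share of that group,

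D_obs = (pc − pe) − g·(px − pe).

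At px = 70% this gives 15 − 0.10 × 32 = 11.8 points for g = 10%, and 15 − 0.20 × 32 = 8.6 points for g = 20%. So patients with the same assumed pain rate widen the contrast under one reading and narrow it under the other.

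**The case against.** A reader might infer that treated patients are being counted as unexposed and that the primary contrast is therefore diluted, with sample-size inflation of 1/(1 − c)² for a contaminated share c: 1.23, 1.56 and 2.04 at 10%, 20% and 30%. The arithmetic is right, but the documents do not support the claim, for four reasons.

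- Section 7 uses start time as the regressor, not the two-group split. For the patients in question the coding is unstated; they are not clearly unexposed.
- The late group is treated by design, since one primary objective compares acute with subacute starting. An untreated comparator is closer to the objective on early use and prevalence.
- Dilution by the factor 1 − c requires misplaced patients to have outcomes like early starters. Pre-injury users may have had pain already, which could widen the contrast.
- The shares are assumed, and with no planned sample size there is no power to preserve.

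It is also fair to say that classing a pregabalin-only patient as not started on gabapentin is correct for a question about gabapentin timing. For that patient the issue is confounding by co-treatment. The visible data list is also an imperfect guide: it omits the gabapentin start date that section 3 says will be recorded, so absence from it is weak evidence, and Figure 2 may contain more.

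These points limit the claim but do not remove it. Nothing in the text defines new-user status, says how the three undefined kinds of patient enter the models, or names home medications for use in grouping. The general confounder rule can reach home medications only by a later choice, and it cannot reach a co-treatment that is not collected.

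**Conclusion.** The point holds as a gap in the exposure definition. On the literal wording, pre-injury gabapentin users sit in the wrong contrast. The start-time regressor is undefined for never-users and pregabalin-only patients and falls before injury for pre-injury users. Pregabalin after injury is a co-treatment that the visible plan does not capture.

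The effect on the early-versus-late contrast may go in either direction, and its size cannot be estimated from the documents. The point differences above show only that the sign is open. They rest on a placeholder comparison rate and on assumed shares and pain rates, and are not a forecast for this study. The statement about missing data fields depends on Figure 2, which is not visible; the statements about grouping and coding do not.

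**What to change.** 1. **New users.** In section 7, restrict the primary gabapentin-timing analyses to new users and non-users. Use the home-medication item already collected to set aside patients on a gabapentinoid before injury. They remain enrolled and are described separately.
2. **Pregabalin.** Add start and stop dates of gabapentin and pregabalin to the chart abstraction. Treat pregabalin after injury as a recorded co-treatment and keep these patients in the primary analysis. If pregabalin tends to be given for worse pain, removing them would select patients on a pain-driven event after injury. Prespecify a sensitivity analysis that puts them in a separate category or leaves them out.
3. **Never-users.** State that they enter the DN4 comparison as a separate category and are not given an assigned start time.

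The cost is a few more fields in a chart review already planned, some added wording in section 7, and slightly fewer patients in the timing analyses. Patient care does not change.

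### Weekly opiate totals counted from injury include opiates given during surgery, with no planned adjustment, so an uneven split of operated patients could confound the early-week MME comparison

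*Combined protocol and SAP*

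**What the plan says.** Section 2 (Endpoints) lists as a secondary endpoint "Weekly total use of opiates (total morphine milligram equivalents, MME". Section 6 (Study methods, additional data collection) gives the abstraction item as "Total weekly MME per week from injury". Section 3 (Design) names the source: "The remainder of the data collection will be through review of the patient's electronic medical record (EMR". None of these limits the count by indication, route, care setting or timing relative to the first gabapentin dose. Section 10 (Study Assessments) adds a change in opiate use, without naming a baseline week.

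The design is "Prospective, observational, cohort, single center study", and exposure is defined by care in the acute hospital: Section 3 groups patients by whether or not their first gabapentin came before transfer to rehabilitation. The end of the Introduction puts opiate use in the study goal, which is whether "early initiation of treatment with gabapentin will decrease average pain scores and opiate use when compared to late initiation".

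Section 7 (Statistical Analysis Plan) describes models for DN4 presence and for NPS change only, and its rule for adding confounders appears under those two. Section 6 does collect "Operative vs nonoperative management of SCI" and the AIS at three times, including the first one on record.

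**The concern.** Counting from injury places the first week or weeks in the acute hospital, where some patients have spinal surgery. Opiates given as part of an anaesthetic reflect the operation, not the patient's pain, but an unrestricted total adds the two together. Exposure is settled, without randomisation, in the same period. If the proportion operated differs between the early and late gabapentin groups, part of any difference in early-week MME would reflect surgery rather than gabapentin timing. If an early week served as the baseline for the change in opiate use, the same doses would produce an apparent fall.

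Lower opiate use is one of the two benefits named in the study goal, and the Introduction says that a positive result would make it reasonable to start gabapentin in all patients without a contraindication. A difference in surgical mix should not be able to pass for that benefit, or hide it.

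**Working it through.** The documents give no MME figure, sample size or rate of surgery by group, so there is nothing to reproduce. The arithmetic below is an illustration, and every input is an assumption.

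**Inputs (assumed)**
- Analgesic use, identical in all patients: 60 MME/day, so 7 × 60 = 420 MME per week.
- Extra non-analgesic opiate in an affected patient, M: three days at 200 MME/day = 600 MME, with a range of 300 (100/day) to 1,200 (400/day).
- Share affected: 30% of one group, 10% of the other.

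**One affected week**
- An affected patient totals 420 + 600 = 1,020 MME, and 1,020 / 420 = 2.43 times the analgesic use.
- The group mean is 420 + share × M:
  - M = 600: 420 + 180 = 600 versus 420 + 60 = 480; ratio 1.25.
  - M = 300: 420 + 90 = 510 versus 420 + 30 = 450; ratio 1.13.
  - M = 1,200: 420 + 360 = 780 versus 420 + 120 = 540; ratio 1.44.
- If the extra opiate replaces the analgesic dosing on those three days (3 × 60 = 180), an affected patient totals 420 − 180 + 600 = 840. The excess is then 420, and the means are 420 + 0.3 × 420 = 546 versus 420 + 0.1 × 420 = 462; ratio 1.18.
- Three days' worth may be generous for a single operation. With M = 100, the means are 450 versus 430, about 5%.

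**Direction**
- In absolute terms, false difference = d × M, where d is the affected share in the early group minus that in the late group. For M between 100 and 1,000 and d between −20 and +30 points, it runs from −0.20 × 1,000 = −200 to +0.30 × 1,000 = +300 MME in the affected week. It is zero when d = 0.

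**Several weeks averaged**
- With M = 600 and only one week affected, four weeks give (600 + 3 × 420) / 4 = 465 versus (480 + 3 × 420) / 4 = 435, or 7%.
- Eight weeks give (600 + 7 × 420) / 8 = 442.5 versus (480 + 7 × 420) / 8 = 427.5, or 3.5%.
- If only rehabilitation weeks are compared, the contribution is about zero, assuming no such use during rehabilitation.

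**Change from the affected week**
- Suppose the early group is the one with 30% affected and later weeks are 420 in both groups. The early group falls by 600 − 420 = 180 and the late group by 480 − 420 = 60. That is a false advantage of 120 MME for early gabapentin, although the same week compared as a level counts against it by 120.

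**Effect of the remedy on these inputs**
- Removing the anaesthesia-record doses gives 420 versus 420.
- If the affected patients are exactly the operated ones, stratifying gives 1,020 versus 1,020 and 420 versus 420, so the false difference disappears within strata.

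**The case against.** The strongest reply is that no bias has been shown. The documents never mention anaesthesia, sedation or ventilation and give no surgery rates by group; with equal shares the effect is zero. This stands, and it limits the point to a risk.

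A reader might infer that the protocol itself says operated patients start gabapentin early, because the Introduction states that "gabapentin given perioperatively leads to reduced opiate use and decreased pain in post-operative period". It does not support that. The sentence summarises published evidence on spine surgery with or without SCI. Where the Introduction describes practice, it ties starting gabapentin to the onset of neuropathic pain.

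Other parts of the reply also stand. The data are separate weekly totals, so contamination stays in the affected weeks, and the plan does not say which weeks are compared. Section 6 refers to a Figure 2 that is not in the text available here; whether it narrows the weeks or sources could not be checked. It is not stated outright that acute-stay anaesthesia records are within the record reviewed, although forming the groups and counting pain scores and MME from injury require acute-stay data. Total opiate exposure is also a legitimate outcome, which is why the unrestricted total should still be reported.

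Extending the exclusion to infusions given during ventilation is harder to defend. Ventilation is not a listed data item, and such infusions may also relieve pain: if the infusion was the patient's analgesia for three days, the assumed inputs would remove 180 of 420 MME, or 43%, and only from ventilated patients.

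None of this answers the central gap. The count is unrestricted and MME has no planned adjusted analysis. Collecting operative status makes adjustment possible but does not commit the plan to it.

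**Conclusion.** The point holds as a modest one. As written, the endpoint counts opiates given during surgery in the acute stay, and the plan has no adjusted MME analysis to deal with an uneven split of operated patients. Early-week comparisons, and any change measured from those weeks, could be confounded.

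A reader might go further and conclude that the groups are unbalanced and the comparison biased. The documents do not support that, since they fix neither the size nor the sign. The 25% figure (13% to 44% over the assumed extra doses) applies to a single week, rests wholly on assumed inputs, and shrinks when weeks are averaged.

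The endpoint is secondary, and the primary DN4 and NPS analyses are unaffected. The case for acting is that opiate use is in the study goal and the remedy is cheap.

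**What to change.** - In Section 2 and Section 6, define the main MME endpoint to exclude opiates charted in the anaesthesia record, and report the unrestricted weekly total as a sensitivity result.
- In Section 7, add an MME comparison by gabapentin timing, stratified by or adjusted for operative versus nonoperative management and the first documented AIS. Both are already collected. State which weeks are compared and which week is the baseline for change.
- Treat exclusion of opiate infusions during mechanical ventilation only as a further sensitivity analysis, since it needs ventilation times that are not now abstracted and may remove real analgesia.

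The cost is slightly more abstraction from records already under review. No new patient contact is needed, and the primary endpoints do not change.
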